## 15.1.5. Change from baseline to week 24 and week 48 in the PROMIS Fatigue Short Form 8a

PROMIS Fatigue Short Form 8a assesses the impact and perceived fatigue during the last 7 days, through 8-question scale with scores ranging from 1 to 5. Scores are converted to a T-score and received within the eCOA transfers. Higher scores indicate higher fatigue levels. A decrease in score (negative change from baseline) indicates improvement in fatigue.

The number and percentage of participants with each PROMIS score will be summarized by treatment and time point, for the FAS. T-scores will be descriptively summarized to present absolute value and changes from baseline for each visit for IA and FPA using the FAS.

## 15.1.6. Change from baseline to week 24 and week 48 in the PROMIS Cognitive Function Short Form 6a

PROMIS Cognitive Function Short Form 6a assesses the frequency of cognitive difficulties experienced in the past 7 days. The questionnaire comprises 6 questions on subjective cognitive difficulties regarding a participant's concentration, memory, language, mental acuity, and perceived changes in cognitive functioning. The participant marks their response on a 5-point Likert scale, with lower scores indicating worse perceived cognitive functioning. Scores are converted to a T-score and received within the eCOA data transfers.

The number and percentage of participants with each individual PROMIS score will be summarized by treatment and time point, for the FAS for the IA. T-score will be descriptively summarized to present absolute value and changes from baseline for each visit.

## 15.2. Pharmacodynamic Analysis

Pharmacodynamic (PD) effect of efgartigimod will be assessed via Total IgG. PD analyses will be performed in the SAF for IA and FPA.

Two analyses will be presented, one using the baseline of the parent study (2104); and the other using the baseline of the present OLE study (2104 week 24 visit/ARGX-113-2105 baseline/day 1).

Total IgG will be summarized using descriptive statistics at each analysis visit. Absolute values, changes from baseline, and percent reduction from baseline will be presented. In addition to the planned time points, the following time points will also be shown:

- Maximum drop from baseline
- Minimum post baseline value

All PD data will be listed.

Document: BIOSdata\argenx\Efgartigimod\HAB40220\Biostatistics\Documentation\SAP

Author: Version Number: 1.0

Version Date: 03 June 2024

Template No.: CS\_TP\_BS016 Revision 7 Reference: CS\_WI\_BS005

Effective Date: 01Nev2021

Page 41 of 54

## 15.3. Pharmacokinetic Analysis

PK analyses will be performed in the PKAS.

At IMP administration visits, PK blood samples will be collected pre-dose, at visits where IMP is not administered (Week 48 and at unscheduled visits) the PK sample can be collected at any time during the visit.

A listing of PK blood sample collection times, derived sampling time deviations, and concentrations will be provided for the PKAS for FPA only.

Serum concentrations will be summarized using descriptive statistics for efgartigimod including the change from baseline and percent reduction. Concentrations that are BLQ will be treated as zero for the computation of descriptive statistics. If at least one BLQ value is reported at a specific time point, the GM and geometric CV% for that time point will not be calculated. The pharmacokineticist will determine a strategy for dealing with data affected by protocol deviations or events which may impact the quality of PK concentration data on a case-by-case basis with input from the study physician, as needed. Examples of protocol deviations or events include, but may not be limited to the following:

- When a predose sample is taken after IMP administration.
- When the most recent IMP administration before the scheduled pre-dose PK sample is missed (not applicable for Day 1).
- Any event related to sample collection, handling and storage that affects the integrity of the samples and/or the bioanalytical results.
- When pre-dose PK samples are taken outside the visit windows.
- The study visit windows are  $\pm 2$  days.

In the case of a protocol deviation or event which may impact the quality of PK, the PK data collected may be excluded from the summaries and a reason for the exclusion of the data point will be added in the appropriate listing.

The strategy for the population PK analysis and any related exposure-response modeling utilizing the efgartigamod concentration and IgG data collected from this study will be outlined separately in the modeling data analysis plan.

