# 9.3. Statistical Analyses

#### 9.3.1. General Considerations

The results of this study will not be used inferentially. No formal sample size calculation is presented.

Summaries will include the number of observations (n), mean, SE, 95% CI, median, minimum, and maximum for continuous measures. Summaries will include sample size, frequencies, and percentages for categorical variables. For categorical variables, participants with missing data will be counted as a separate category; proportions will be calculated using as denominator all enrolled participants.

All study visits will be recalculated based on actual dates. The rules for calculating the analysis visits and for imputing partial dates or missing dates will be documented in the SAP.

Summaries will be provided both for the overall study population as well as grouped according to treatment received in Study ARGX-113-2104 (efgartigimod or placebo).

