### 6.2. Baseline

Unless otherwise specified, baseline is defined as the last available non-missing measurement per parameter from the parent study 2104. Refer to appendix 1 baseline for details.

Assessments performed on the same day as the first IMP administration but without time information collected or with time information exactly equal to the time of first IMP administration and which are planned predose will be considered as predose.

Adverse Events (AEs) and medications commencing on the reference start date will be considered post-baseline unless otherwise indicated based on available start date/time combination or collected electronic case report form (eCRF) information that identifies the individual event/medication as starting prior to first IMP administration.

The baseline visit for Study 2105 will be conducted after the participant has finished in 2104 and completed week 24

Document: BIOSdata\argenx\Efgartigimod\HAB40220\Biostatistics\Documentation\SAP

1.0 Author: Version Number:

> Version Date: 03 June 2024

Template No.: CS\_TP\_BS016 Revision 7 Reference: CS\_WI\_BS005

analysis. All baseline assessments will be performed before first administration of efgartigimod IV in ARGX-113-2105, if applicable. Assessments do not need to be repeated if they are performed as part of 2104.

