## 6.7. Values below or Above the Quantification Limit

- ADA against efgartigimod: titer of positive ADA samples reported as "negative titer" will be imputed by 1. Listings will always present "negative titer".
- Safety and PD values expressed as below (or above) the quantification limit will be imputed by the
  value of the quantification limit itself. For participants with a baseline PD value below/above the
  quantification limit, the PD parameter will be excluded from the statistical analyses involving
  change and percent change from baseline. Listings will always show the non-imputed values.
- Pharmacokinetic concentrations below the lower quantification limit will be reported in the listings as BLQ. For descriptive statistical analysis, all BLQ values will be set to zero. Listings will always present BLQ.

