### 6.8. Common Calculations

For quantitative measurements, change from baseline will be calculated as:

 $\circ$  Change from baseline at Visit X = Value at Visit X – baseline value.

A percent change from baseline can be calculated as;

• Percent change from baseline at Visit X = (actual value at Visit X -baseline value) \*100/baseline value.

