## 7.2. Output Presentation

For continuous variables, full descriptive statistics will only be presented if there are at least 2 non-missing observations. Alternatively, only the number of non-missing data points and mean are shown. In tables by analysis visit, only analysis visits with at least 10 participants (overall) will be shown.

Descriptive statistics for safety and efficacy will include the number of non-missing data points, the arithmetic mean, the standard deviation (SD), the median, minimum, Q1, Q3, maximum, and for efficacy the standard error (SE) and 95% CI may be provided in addition (refer to output templates for details).

Mean, Q1, Q3 and median will be presented with one more decimal place than the measured values. SE and SD will be presented with two more decimal places than the measured values. Minimum and maximum will be presented with the same number of decimal places as the measured values.

Descriptive statistics for PD parameters will include the number of non-missing data points, the arithmetic mean, the SD, the SE, the 95% CI, the median, minimum, Q1, Q3, and maximum. Descriptive statistics of total IgG levels will be presented in  $\mu g/mL$ .

Descriptive statistics for PK serum concentrations will include the number of observed values, arithmetic mean, SD, median, minimum and maximum, CV%, the GM, and geometric CV%. Serum concentrations will be reported as received by the bioanalytical laboratory.

Descriptive statistics for PK concentrations will be presented with 3 significant digits in  $\mu$ g/mL for efgartigimod (where appropriate), except values  $\geq$ 1000 which will be presented without the decimals and rounded to the nearest integer. If at least one BLQ value is reported at a specific time point, the GM and geometric CV% for that time point will not be calculated. In addition, if more than half of the values per time point are BLQ, the arithmetic mean will be reported as BLQ and SD, CV%, GM, and geometric CV% will not be calculated.

Descriptive statistics for immunogenicity titer values will include the number of observed values, arithmetic mean, SE, 95% CI, median, Q1, Q3, minimum, maximum, the GM, and geometric CV%.

For event-type safety data, the number and percentage of participants with an event will be shown. The denominator will be all participants in the analysis set per treatment.

Document: BIOSdata\argenx\Efgartigimod\HAB40220\Biostatistics\Documentation\SAP

Author: Version Number: 1.0

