#### **Baseline**

Baseline for these data will integrate from the latest non-missing data of 2104 to baseline visit of 2105.

Description		Source
	 	

Document: BIOSdata\argenx\Efgartigimod\HAB40220\Biostatistics\Documentation\SAP

Author: Version Number: 1.0

Version Date: 03 June 2024

Template No.: CS\_TP\_BS016 Revision 7 Reference: CS\_WI\_BS005

Effective Date: 01Nov2021

Copyright © 2009, 2010, 2012, 2016, 2018, 2019, 2021 IQVIA. All rights reserved. The contents of this document are confidential and proprietary to IQVIA Holdings Inc. and its subsidiaries. Unauthorized use, disclosure or reproduction is strictly prohibited.

Page 50 of 54

Physical Examination	EDC data: PE1
ECG	EDC data: EG
	Non-EDC data: ECG
Laboratory Assessment - Hematology and Chemistry	EDC data: LB
	Non-EDC data: Q  S (and RBM)
Laboratory Assessment: Immunogenicity Sample	EDC data: LB_IMMUNO
	Non-EDC data: Q  S (and RBM)
Laboratory Assessment: Biomarker Sample	EDC data: LB_MI_BIO
	Non-EDC data: Q  S (and RBM)
Lab Page - Urinalysis	EDC data: LB1
	Non-EDC data: Q  S (and RBM)
Lab Page - TSH/CRP/ESR	EDC data: LB2
	Non-EDC data: Q  S (and RBM)
Pharmacokinetics Concentration	EDC data: PC1
	Non-EDC data: PK
Pharmacodynamics	EDC data: PD
	Non-EDC data: Q  S (and RBM)
Pregnancy Testing	EDC data: PREG
ADA	Non-EDC data: ADA
eCOA	Non-EDC data: eCOA

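### SAP 15.3 asks for percent reduction in efgartigimod concentration, which is undefined for prior-placebo participants and otherwise mostly reflects the planned move from weekly to two-weekly dosing

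*SAP*

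**What the plan says.** On drug concentration, SAP 15.3 (Pharmacokinetic Analysis) says: "Serum concentrations will be summarized using descriptive statistics for efgartigimod including the change from baseline and percent reduction".

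Four other SAP rules determine what that produces:

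- **Baseline.** In SAP 6.2, "baseline is defined as the last available non-missing measurement per parameter from the parent study 2104". SAP Appendix 1 lists PK concentration among the data for which "Baseline for these data will integrate from the latest non-missing data of 2104 to baseline visit of 2105". Protocol Table 1 takes this sample at the 2104 Week 24 assessment, before the first extension dose.
- **Formula.** SAP 6.8 defines percent change with baseline as the divisor: "actual value at Visit X -baseline value) \*100/baseline value". It does not define percent reduction separately.
- **Values below quantification (BLQ).** For PK, SAP 6.7 says: "For descriptive statistical analysis, all BLQ values will be set to zero".
- **BLQ baselines.** SAP 6.7 has an exclusion for PD: "the PD parameter will be excluded from the statistical analyses involving" change and percent change. It has no counterpart for PK.

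Protocol 9.3.3.3 asks only for descriptive statistics of concentrations and for troughs, leaving the trough details to the SAP. Percent reduction from baseline appears in Protocol Table 3 as the total IgG endpoint. Protocol 9.3.1 adds: "Summaries will be provided both for the overall study population as well as grouped according to treatment received" in study 2104.

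The SAP splits exposure by dosing regimen (section 12), and COMPASS 31 and MaPS by whether the participant went back to QW (15.1.1, 15.1.2). Section 15.3 names no such split.

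**The concern.** Percent reduction from baseline suits IgG, which starts high in untreated participants and is meant to fall. Drug concentration starts at zero in untreated participants, so the same statistic has no denominator for one parent arm.

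For the other parent arm, baseline is a trough on weekly dosing. Most later samples are troughs on two-weekly dosing, so the percentage mainly restates the schedule.

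What is at stake is the clarity of one exposure table: what its overall column describes, and whether a step between Week 4 and Week 12 is recognised as planned. A smaller, related issue is that the later visits combine 14-day troughs (Q2W) with 7-day troughs (participants back on QW).

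**Working it through.** There is no stated figure to reproduce. The schedule arithmetic (day = 7 × week + 1) does reproduce the protocol's days 323, 330 and 337 for Weeks 46, 47 and 48.

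**1. Who is affected.** Protocol 9.5 expects about 38 participants, at about 90% of the parent study. The parent size is not given. Back-calculated, 38/0.90 = 42.2, so about 42 (an assumption). Allocation 2:1 (Protocol 2) gives 28 and 14. If 2:1 holds at rollover, prior placebo is 38/3 = 12.7, about 13, and prior efgartigimod about 25. If the 4 who do not roll over all came from one arm, the ranges are 10–14 and 24–28. PK summaries use the PK analysis set, which may be smaller. That set requires only a concentration after the start of dosing, so it does not remove prior-placebo participants as such.

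**2. Prior placebo.** No efgartigimod has been given by 2104 Week 24, so a BLQ baseline is expected and is set to 0. Percent change is (C − 0) × 100/0, undefined at all five post-baseline PK visits.

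**3. Days since last dose at each scheduled PK sample.** The last 2104 dose is at Week 23 (Protocol 2); extension doses are those of Table 1.

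| Sample | On Q2W | Back on QW |
|---|---|---|
| Baseline | 7 | n/a |
| Week 1 | 7 | n/a |
| Week 4 | 29 − 22 = 7 | n/a |
| Week 12 | 85 − 71 = 14 | 7 |
| Week 24 | 169 − 155 = 14 | 7 |
| Week 48 | 337 − 323 = 14 | 337 − 330 = 7 |

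**4. Expected percent reduction, prior efgartigimod on Q2W, pharmacokinetics unchanged.** The mg/kg dose is the same throughout (Protocol 4.3). With one-compartment decay and x = 2^(−7/half-life), the steady-state trough is proportional to x/(1 − x) on QW and x²/(1 − x²) on Q2W. The reduction is 1 − x/(1 + x) = 1/(1 + x). Half-life is not in the documents, so a range is assumed. Summing 24 weekly parent doses and the extension schedule gives:

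| Half-life (days) | x | Weeks 1, 4 | Week 12 | Week 24 | Week 48 |
|---|---|---|---|---|---|
| 3 | 0.198 | 0% | 83.4% | 83.4% | 83.4% |
| 7 | 0.500 | 0% | 66.4% | 66.7% | 66.7% |
| 14 | 0.707 | 0% | 54.9% | 58.5% | 58.6% |

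A lower bound needs less. Under linear kinetics with any declining single-dose curve, the QW trough sums C(7) + C(14) + C(21) + C(28) + …, and the Q2W trough keeps only C(14) + C(28) + …. Each kept term is no larger than the dropped term before it, so the steady-state reduction is at least 50%. Participants back on QW return to about 0%.

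The 0% at Weeks 1 and 4 is for on-schedule samples. With a 3-day half-life, taking only the baseline sample 2 days early or late multiplies it by 2^(2/3) = 1.59 or divides it by that. An individual Week 1 value would then be 1 − 1/1.59 = +37% or 1 − 1.59 = −59%.

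**5. Overall mean absolute change**, in units of the prior-efgartigimod baseline trough: (25 × change in prior efgartigimod + 13 × change in prior placebo)/38. At a 7-day half-life:

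- Week 4: (25 × 0 + 13 × 0.94)/38 = +0.32
- Week 24: (25 × (−0.667) + 13 × 0.333)/38 = −0.32

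For half-lives of 3 to 14 days the range is +0.34 to +0.26 at Week 4 and −0.49 to −0.24 at Week 24. At Week 24 in this example both arms have the same trough (0.333), yet one shows a rise and the other a fall.

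**6. Baseline display.** Overall, 13/38 = 34% BLQ is under half, so a mean including zeros is shown. In the prior-placebo column SAP 7.2 applies: "if more than half of the values per time point are BLQ, the arithmetic mean will be reported as BLQ".

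**7. Regimen mixing at Week 24.** The QW/Q2W trough ratio R is 6.04, 3.00 and 2.41 at half-lives of 3, 7 and 14 days. If a share f is back on QW, the pooled mean divided by the Q2W mean is 1 + f(R − 1): 1.14 to 1.50 at f = 10%, and 1.56 to 3.02 at f = 40%. If the two groups do not overlap, the pooled median falls at the 0.5/(1 − f) quantile of the Q2W values: the 56th percentile at f = 10% and the 83rd at 40%. The documents do not give f.

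**The case against.** The best defence is that a table built to the rules would explain itself. Protocol 9.3.1 requires parent-arm columns as well as an overall column, and SAP 7.2 requires the number of observed values for PK. SAP 7.1 does not impute, so undefined percentages drop out: n would be 0 for prior placebo and the overall n would be visibly reduced. A reader might infer that the plan conceals a one-arm result. The documents do not support that. The defence is incomplete only because 15.3 does not repeat the parent-arm split and SAP Appendix 1 shows a single treatment group.

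A reader might also infer that the step after Week 4 will be taken for exposure drifting down. That is speculative: the change to Q2W is the stated design, SAP 15.5 tabulates regimen by visit, and 15.3 lists sample times.

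A third tempting inference is that the PD exclusion in SAP 6.7 should be copied to absolute change in concentration. It should not. PD values below quantification are set to the limit, PK values to zero, and a change from zero is computable and interpretable. Excluding it would discard valid data from about a third of participants. The problem lies in pooling it across arms.

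Finally, the protocol requires no PK table by regimen. Protocol 9.3.3.6 leaves further regimen analysis optional, and a population PK/PD analysis has its own plan. This stands: the regimen split is an improvement, and without f its benefit cannot be sized.

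**Conclusion.** The point holds, at minor severity. That percent reduction is undefined for prior-placebo participants follows from the SAP's own baseline, BLQ and formula rules, given that these participants have no quantifiable drug before their first active dose. The count of about 13 of 38 assumes 2:1 at rollover and no PK analysis set exclusions.

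For prior-efgartigimod participants on Q2W, the planned interval change alone gives a reduction of at least 50% at Q2W steady state under linear kinetics, and 55% to 83% over Weeks 12 to 48 at assumed half-lives of 14 to 3 days. The 50% bound is a steady-state result; with a half-life beyond the assumed range, Week 12 could fall below it.

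An overall percent reduction thus describes the prior-efgartigimod arm only, and an overall mean change mixes rises from zero with planned falls. It would be too much to read this as a threat to the exposure endpoint: concentration summaries and listings remain, and no safety or efficacy conclusion rests on the affected output.

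**What to change.** In SAP 15.3:

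- **Percent reduction.** Delete it for PK, or show it only for participants with a quantifiable baseline, labelled as prior-efgartigimod and with n.
- **Absolute change.** Delete it for PK, or show it by parent arm only, keeping BLQ baselines as zero and giving no pooled figure.
- **Cheap addition.** Summarise scheduled trough concentrations by visit and by regimen at that visit (Q2W or QW), as a one-way split alongside the overall and parent-arm summaries.
- **Unscheduled samples.** SAP 6.3 allocates unscheduled assessments to analysis windows. If samples from the unscheduled dosing-switch visit are to stay out of the by-visit trough summaries, state this as an explicit exception.

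The cost is SAP wording and possibly table shells, which are not in the documents. Dosing times, sample times and switch dates are already recorded. The drawback of the regimen split is a small QW cell: about 4 of 38 at f = 10%, 15 at 40%. With fewer than 2 values, SAP 7.2 shows only n and the mean. If few participants switch, the gain is small.

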## 15.4. Immunogenicity Analysis

Incidence and prevalence of antidrug antibodies (ADA) against efgartigimod will be assessed in the SAF for the FPA. ADAs to efgartigimod is measured at the time points specified in the schedule of activities of protocol, primarily at baseline, week 1, 4, 12, 24, 48 and SFV.

Immunogenicity samples are analyzed in a 3-tiered approach:

- All samples are evaluated in the ADA screening assay and are scored ADA screening positive (tier 1) or negative.
- If a sample is scored positive in the ADA screening assay, it is further evaluated in the confirmatory assay (tier 2) and is scored confirmed positive (positive immuno-depletion) or confirmed negative

Document: BIOSdata\argenx\Efgartigimod\HAB40220\Biostatistics\Documentation\SAP

Author: Version Number: 1.0

Version Date: 03 June 2024

Template No.: CS\_TP\_BS016 Revision 7 Reference: CS\_WI\_BS005

Page 42 of 54

(negative immuno-depletion).

• If a sample is scored as confirmed positive, the samples are further characterized in the ADA titration assay (to determine titer).

If available, a titer result will be reported for the ADA confirmed positive samples. However, a titer result is not always available:

- If the ADA confirmed positive sample could not be run in the titration assay (e.g., due to insufficient sample volume/quality to perform the titer analysis), the result will be described as "positive immunodepletion", and the sample should be considered ADA positive.
- If a sample is negative in the titration assay, it will be reported as "negative titer", but it should be considered ADA positive because it was confirmed positive in the second tier.
- If a sample could not be analyzed or reported as "positive screen", the ADA sample status is ADA unevaluable.

An overview of this 3-tiered approach and all possible ADA sample results that will be reported by the laboratory is given below. From these reported ADA sample results, a final ADA sample status must be derived during the statistical analysis, as presented in the final column ("Final ADA Outcome"):

Document: BIOSdata\argenx\Efgartigimod\HAB40220\Biostatistics\Documentation\SAP

[figure not shown]
Author: Version Number: 1.0

Version Date: 03 June 2024

Template No.: CS TP BS016 Revision 7 Reference: CS WI BS005

Page 43 of 54

Figure 1: ADA Sample Status

<sup>a "Positive titer" is reported if it was not possible to retrieve a numerical value.

